10.3.5 Reporting of AEs, SAEs, and Other Reportable Safety Events to the Sponsor

AE, SAE, and other reportable safety event reporting to Sponsor via electronic data collection tool

- The primary mechanism for reporting to the Sponsor will be the electronic data collection (EDC) tool.
 - Electronic reporting procedures can be found in the EDC data entry guidelines (or equivalent).
 - If the electronic system is unavailable for more than 24 hours, then the site will use the paper AE Reporting form.
 - Reference Section 8.4.1 for reporting time requirements.
- The site will enter the SAE data into the electronic system as soon as it becomes available.
- After the study is completed at a given site, the EDC tool will be taken off-line to prevent the entry of new data or changes to existing data.
- If a site receives a report of a new SAE from a study participant or receives updated data on a previously reported SAE after the EDC tool has been taken off-line, then the site can report this information on a paper SAE form or by telephone (see next section).
- Contacts for SAE reporting can be found in the Investigator Study File Binder (or equivalent).

SAE reporting to the Sponsor via paper CRF

- If the EDC tool is not operational, facsimile transmission or secure e-mail of the SAE paper CRF is the preferred method to transmit this information to the Sponsor.
- In rare circumstances and in the absence of facsimile equipment, notification by telephone is acceptable with a copy of the SAE data collection tool sent by overnight mail or courier service.
- Initial notification via telephone does not replace the need for the investigator to complete and sign the SAE CRF pages within the designated reporting time frames.
- Contacts and instructions for SAE reporting and paper reporting procedures can be found in the Investigator Study File Binder (or equivalent).

10.4 Appendix 4: Device Events, Adverse Device Events, and Medical Device Incidents: Definitions, Collection, and Documentation

Not applicable.

10.5 Appendix 5: Contraceptive Guidance and Pregnancy Testing

10.5.1 Definitions

Women of Childbearing Potential (WOCBP)

A woman is considered fertile following menarche and until becoming postmenopausal unless permanently sterile (see below):

If fertility is unclear (eg, amenorrhea in adolescents or athletes) and a menstrual cycle cannot be confirmed before first dose of study intervention, additional evaluation should be considered.

Women in the following categories are not considered WOCBP:

- Premenarchal
- Premenopausal female with 1 of the following:
 - Documented hysterectomy
 - Documented bilateral salpingectomy
 - Documented bilateral oophorectomy

For individuals with permanent infertility due to an alternate medical cause other than the above (eg, Mullerian agenesis, androgen insensitivity), investigator discretion should be applied to determining study entry.

Note: Documentation can come from the site personnel's review of the participant's medical records, medical examination, or medical history interview.

- Postmenopausal female
 - A postmenopausal state is defined as no menses for 12 months without an alternative medical cause.
 - A high follicle stimulating hormone (FSH) level in the postmenopausal range may be used to confirm a postmenopausal state in women not using hormonal contraception or hormone replacement therapy (HRT). However, in the absence of 12 months of amenorrhea, confirmation with two FSH measurements in the postmenopausal range is required.
 - Females on HRT and whose menopausal status is in doubt will be required to use one of the nonhormonal highly effective contraception methods if they wish to continue their HRT during the study. Otherwise, they must discontinue HRT to allow confirmation of postmenopausal status before study enrollment.

10.5.2 Contraception Requirements

Female Participants

Contraceptives allowed during the study include^a:
Highly Effective Contraceptive Methods That Have Low User Dependency^b Failure rate of <1% per year when used consistently and correctly.

• Progestogen- only contraceptive implant^c• Intrauterine hormone-releasing system (IUS)^c (IUS is a progestin releasing IUD)• Intrauterine device (IUD)• Bilateral tubal occlusion

• Azoospermic partner (vasectomized or secondary to medical cause) This is a highly effective contraception method provided that the partner is the sole male sexual partner of the WOCBP and the absence of sperm has been confirmed. If not, an additional highly effective method of contraception should be used. A spermatogenesis cycle is approximately 90 days.

Note: Documentation of azoospermia can come from the site personnel's review of the participant's medical records, medical examination, or medical history interview.

Highly Effective Contraceptive Methods That Are User Dependent^b Failure rate of <1% per year when used consistently and correctly.

• Combined (estrogen- and progestogen-containing) hormonal contraception
- Oral- Intravaginal- Transdermal- Injectable• Progestogen-only hormonal contraception
- Oral- Injectable
Sexual Abstinence 
• Sexual abstinence is considered a highly effective method only if defined as refraining from heterosexual intercourse during the entire period of risk associated with the study intervention. The reliability of sexual abstinence needs to be evaluated in relation to the duration of the study and the preferred and usual lifestyle of the participant.
Acceptable Contraceptive Methods Failure rate of >1% per year when used consistently and correctly.

• Progesterone-only hormonal contraception where inhibition of ovulation is not the primary mode of action• Male or female condom with or without spermicide• Cervical cap, diaphragm, or sponge with spermicide• A combination of male condom with either cervical cap, diaphragm, or sponge with spermicide (double barrier methods)^d 
a. Contraceptive use by men or women should be consistent with local regulations regarding the use of contraceptive methods for participants of clinical studies.b. Typical use failure rates are higher than perfect-use failure rates (ie, when used consistently and correctly).c. If locally required, in accordance with Clinical Trial Facilitation Group (CTFG) guidelines, acceptable contraceptive implants are limited to those which inhibit ovulationd. A combination of male condom with either cap, diaphragm, or sponge with spermicide are considered acceptable, but not highly effective, birth control methods.

Note: The following are not acceptable methods of contraception:
 
- Periodic abstinence (calendar, symptothermal, post-ovulation methods), withdrawal (coitus interruptus), spermicides only, and lactational amenorrhea method (LAM).- Male and female condom should not be used together (due to risk of failure with friction).

10.5.3 Pregnancy Testing

WOCBP should only be included after a negative highly sensitive urine or serum pregnancy test.

Pregnancy testing will be performed whenever an expected menstrual cycle is missed or when pregnancy is otherwise suspected.

10.6 Appendix 6: Collection and Management of Specimens for Future Biomedical Research

- **Definitions**

- Biomarker: A biological molecule found in blood, other body fluids, or tissues that is a sign of a normal or abnormal process or of a condition or disease. A biomarker may be used to see how well the body responds to a treatment for a disease or condition.¹
- Pharmacogenomics: The investigation of variations of DNA and RNA characteristics as related to drug/vaccine response.²
- Pharmacogenetics: A subset of pharmacogenomics, pharmacogenetics is the influence of variations in DNA sequence on drug/vaccine response.²
- DNA: Deoxyribonucleic acid.
- RNA: Ribonucleic acid.

- **Scope of Future Biomedical Research**

The specimens consented and/or collected in this study as outlined in Section 8.8 will be used in various experiments to understand:

- The biology of how drugs/vaccines work
- Biomarkers responsible for how a drug/vaccine enters and is removed by the body
- Other pathways drugs/vaccines may interact with
- The biology of disease
- The specimen(s) may be used for future assay development and/or drug/vaccine development.

It is now well recognized that information obtained from studying and testing clinical specimens offers unique opportunities to enhance our understanding of how individuals respond to drugs/vaccines, enhance our understanding of human disease and ultimately improve public health through development of novel treatments targeted to populations with the greatest need. All specimens will be used by the Sponsor or those working for or with the Sponsor.

- **Summary of Procedures for Future Biomedical Research.**

1. Participants for Enrollment

All participants enrolled in the clinical study will be considered for enrollment in future biomedical research

2. Informed Consent

Informed consent for specimens (ie, DNA, RNA, protein, etc.) will be obtained during screening for protocol enrollment from all participants or legal guardians, at a study visit by the investigator or his or her designate. Informed consent for future biomedical research should be presented to the participants on the visit designated in the SoA. If delayed, present consent at next possible Participant Visit. Consent forms signed by the participant will be kept at the clinical study site under secure storage for regulatory reasons.

A template of each study site's approved informed consent will be stored in the Sponsor's clinical document repository.

3. eCRF Documentation for Future Biomedical Research Specimens

Documentation of participant consent for future biomedical research will be captured in the eCRFs. Any specimens for which such an informed consent cannot be verified will be destroyed.

4. Future Biomedical Research Specimen(s)

Collection of specimens for future biomedical research will be performed as outlined in the SoA. In general, if additional blood specimens are being collected for future biomedical research, these will usually be obtained at a time when the participant is having blood drawn for other study purposes.

- **Confidential Participant Information for Future Biomedical Research**

In order to optimize the research that can be conducted with future biomedical research specimens, it is critical to link participant' clinical information with future test results. In fact little or no research can be conducted without connecting the clinical study data to the specimen. The clinical data allow specific analyses to be conducted. Knowing participant characteristics like gender, age, medical history and intervention outcomes are critical to understanding clinical context of analytical results.

To maintain privacy of information collected from specimens obtained for future biomedical research, the Sponsor has developed secure policies and procedures. All specimens will be single-coded per ICH E15 guidelines as described below.

At the clinical study site, unique codes will be placed on the future biomedical research specimens. This code is a random number which does not contain any personally

identifying information embedded within it. The link (or key) between participant identifiers and this unique code will be held at the study site. No personal identifiers will appear on the specimen tube.

- **Biorepository Specimen Usage**

Specimens obtained for the Sponsor will be used for analyses using good scientific practices. Analyses utilizing the future biomedical research specimens may be performed by the Sponsor, or an additional third party (eg, a university investigator) designated by the Sponsor. The investigator conducting the analysis will follow the Sponsor's privacy and confidentiality requirements. Any contracted third party analyses will conform to the specific scope of analysis outlined in future biomedical research protocol and consent. Future biomedical research specimens remaining with the third party after specific analysis is performed will be reported to the Sponsor.

- **Withdrawal From Future Biomedical Research**

Participants may withdraw their consent for future biomedical research and ask that their biospecimens not be used for future biomedical research. Participants may withdraw consent at any time by contacting the principal investigator for the main study. If medical records for the main study are still available, the investigator will contact the Sponsor using the designated mailbox ([contact]).

Subsequently, the participant's specimens will be flagged in the biorepository and restricted to main study use only. If specimens were collected from study participants specifically for future biomedical research, these specimens will be removed from the biorepository and destroyed. Documentation will be sent to the investigator confirming withdrawal and/or destruction, if applicable. It is the responsibility of the investigator to inform the participant of completion of the withdrawal and/or destruction, if applicable. Any analyses in progress at the time of request for withdrawal/destruction or already performed prior to the request being received by the Sponsor will continue to be used as part of the overall research study data and results. No new analyses would be generated after the request is received.

In the event that the medical records for the main study are no longer available (eg, if the investigator is no longer required by regulatory authorities to retain the main study records) or the specimens have been completely anonymized, there will no longer be a link between the participant's personal information and their specimens. In this situation, the request for withdrawal of consent and/or destruction cannot be processed.

- **Retention of Specimens**

Future biomedical research specimens will be stored in the biorepository for potential analysis for up to 20 years from the end of the main study. Specimens may be stored for longer if a regulatory or governmental authority has active questions that are being answered. In this special circumstance, specimens will be stored until these questions have been adequately addressed.

Specimens from the study site will be shipped to a central laboratory and then shipped to the Sponsor-designated biorepository. If a central laboratory is not utilized in a particular study, the study site will ship directly to the Sponsor-designated biorepository. The specimens will be stored under strict supervision in a limited access facility which operates to assure the integrity of the specimens. Specimens will be destroyed according to Sponsor policies and procedures and this destruction will be documented in the biorepository database.

- **Data Security**

Databases containing specimen information and test results are accessible only to the authorized Sponsor representatives and the designated study administrator research personnel and/or collaborators. Database user authentication is highly secure, and is accomplished using network security policies and practices based on international standards to protect against unauthorized access.

- **Reporting of Future Biomedical Research Data to Participants**

No information obtained from exploratory laboratory studies will be reported to the participant, family, or physicians. Principle reasons not to inform or return results to the participant include: Lack of relevance to participant health, limitations of predictive capability, and concerns regarding misinterpretation.

If important research findings are discovered, the Sponsor may publish results, present results in national meetings, and make results accessible on a public website in order to rapidly report this information to doctors and participants. Participants will not be identified by name in any published reports about this study or in any other scientific publication or presentation.

- **Future Biomedical Research Study Population**

Every effort will be made to recruit all participants diagnosed and treated on Sponsor clinical studies for future biomedical research.

- **Risks Versus Benefits of Future Biomedical Research**

For future biomedical research, risks to the participant have been minimized and are described in the future biomedical research informed consent.

The Sponsor has developed strict security, policies, and procedures to address participant data privacy concerns. Data privacy risks are largely limited to rare situations involving possible breach of confidentiality. In this highly unlikely situation, there is risk that the information, like all medical information, may be misused.

- **Questions**

Any questions related to the future biomedical research should be emailed directly to [contact].

- **References**

1. National Cancer Institute [Internet]: Available from <https://www.cancer.gov/publications/dictionaries/cancer-terms?cdrid=45618>
2. International Conference on Harmonization [Internet]: E15: Definitions for Genomic Biomarkers, Pharmacogenomics, Pharmacogenetics, Genomic Data and Sample Coding Categories. Available from <http://www.ich.org/products/guidelines/efficacy/efficacy-single/article/definitions-for-genomic-biomarkers-pharmacogenomics-pharmacogenetics-genomic-data-and-sample-cod.html>
3. Industry Pharmacogenomics Working Group [Internet]: Understanding the Intent, Scope and Public Health Benefits of Exploratory Biomarker Research: A Guide for IRBs/IECs and Investigational Site Staff. Available at <http://i-pwg.org/>
4. Industry Pharmacogenomics Working Group [Internet]: Pharmacogenomics Informational Brochure for IRBs/IECs and Investigational Site Staff. Available at <http://i-pwg.org/>

10.7 Appendix 7: Country-specific Requirements

10.7.1 Country-Specific Request by Pharmaceuticals and Medical Devices Agency (PMDA) for Japan

10.7.1.1 Objectives

In addition to the objectives detailed in Section 3, the following objectives are planned:

Objective (Participants ≥ 65 years of age only): To evaluate the safety and tolerability of V114 with respect to the proportion of participants with AEs.

Objective (Participants ≥ 65 years of age only): To compare the serotype-specific OPA GMTs at 30 days postvaccination (Day 30) with V114 versus Prevnar 13TM.

Hypothesis (H1): V114 is **noninferior** to Prevnar 13TM as measured by serotype-specific OPA GMTs for 13 shared serotypes at 30 days postvaccination.

Hypothesis (H2): V114 is **superior** to Prevnar 13TM as measured by serotype-specific OPA GMTs for 2 unique serotypes in V114 at 30 days postvaccination.

Objective (Participants ≥ 65 years of age only): To compare serotype-specific proportions of participants with a ≥ 4 -fold rise from prevaccination (Day 1) to 30 days postvaccination (Day 30) for OPA responses for the 2 unique serotypes in V114 for participants administered V114 versus participants administered Prevnar 13TM.

Hypothesis (H3): V114 is **superior** to Prevnar 13TM for the 2 unique serotypes in V114 based on proportions of participants with a ≥ 4 -fold rise from prevaccination (Day 1) to 30 days postvaccination (Day 30) for serotype-specific OPA responses.

Comparisons for these objectives will use the same criteria used to assess the primary endpoints as detailed in Section 9.6.1 and Section 9.6.2.

10.7.1.2 Statistical Analysis Plan

Immunogenicity and safety analysis endpoints for Japan-specific requirements are similar to those in all the participants. Details are described in Section 9.4.

Statistical testing and inference for immunogenicity and safety analyses are described in Section 9.6.1 and Section 9.6.2, respectively.

10.7.1.3 Sample Size and Power for Immunogenicity Analyses

To accommodate additional requests from the PMDA, at least 800 of the 1200 randomized participants will be ≥ 65 years of age. It is anticipated that 240 participants will be enrolled in Japan, all of whom will be ≥ 65 years of age.

Details of power for the overall study (based on 1200 randomized participants) are described in Section 9.9.1. For participants ≥ 65 years of age, the power is 87.7% for demonstrating noninferiority to Prevnar 13™ for the 13 shared serotypes and superiority for the 2 unique serotypes based on OPA GMTs, conditional on the total planned sample size being able to meet the primary immunogenicity objectives described in Section 3. The 1-sided alpha-level is controlled at 2.5%. The other assumptions for sample size and power calculation are similar to the assumptions for the overall power calculation (see Section 9.9.1 for details).

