Multiplicity	
The study will be considered to have met its primary immunogenicity objectives if noninferiority is demonstrated with respect to OPA GMTs for the 13 shared serotypes and superiority is demonstrated with respect to both OPA GMTs and the proportions of participants with ≥ 4-fold rises in OPA responses for the 2 unique serotypes. Since comparisons are made individually for each of the 15 serotypes, this approach controls the 1-sided type-I error rate at 0.025, and no multiplicity adjustment is required.
 
No multiplicity adjustments will be made for the safety comparisons.

Sample Size and Power	This study will randomize approximately 600 participants into the V114 group and 600 participants into the Prevnar 13™ group. The overall power for all the primary hypotheses is >90% at an overall 1-sided 2.5% alpha-level.
------------------------------	--

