9.8 Multiplicity

The study will have met its primary immunogenicity objectives if noninferiority is demonstrated with respect to the OPA GMTs for the 13 shared serotypes and superiority is demonstrated with respect to both OPA GMTs and the proportions of participants with ≥ 4 -fold rises in OPA responses for the 2 unique serotypes. All hypotheses will be tested individually for each serotype at a 1-sided 0.025 alpha-level. This approach controls the 1-sided type-I error rate at 0.025, and no multiplicity adjustment will be required.

No multiplicity adjustments will be made for the safety comparisons.

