9.9 Sample Size and Power Calculations

9.9.1 Sample Size and Power for Immunogenicity Analyses

This study will randomize approximately 600 participants into the V114 group and 600 participants into the Prevnar 13™ group and has >90% power for demonstrating noninferiority to Prevnar 13™ for the 13 shared serotypes and superiority for the 2 unique serotypes for V114 at an overall 1-sided 2.5% alpha-level. Sample size is also driven by country-specific requirements (see Appendix 10.7 for details).

The sample size and power calculations are based on the following assumptions:

- 90% evaluability rate (approximately 540 evaluable participants per treatment group).
- The underlying serotype-specific OPA GMT ratios (V114/Prevnar 13™) for the 15 pneumococcal serotypes are the same as that observed in V114-006, which range from 0.78 to 1.86 across the shared serotypes and >6.0 for the V114 unique serotypes.
- The underlying differences (V114 - Prevnar 13™) between proportions of participants with a ≥ 4 -fold rise from prevaccination (Day 1) to 30 days postvaccination (Day 30) for OPA responses are the same as that observed in V114-006 for the V114 unique serotypes, which are >0.1.
- The variabilities for OPA titers in both the V114 group and Prevnar 13™ group are the same as those observed in V114-006. That is, the standard deviations of the natural log titers for the 15 pneumococcal serotypes range from 1.33 to 2.24 for V114 and range from 1.37 to 2.25 for Prevnar 13™.
- The statistical criteria for noninferiority and superiority require the lower bound of the 2-sided 95% CI of the OPA GMT ratio (V114/ Prevnar 13™) to be greater than 0.50 and 2.0, respectively.
- The statistical criterion for superiority requires the lower bound of the 2-sided 95% CI of the difference (V114 - Prevnar 13™) in the proportion of participants with a ≥ 4 -fold rise in OPA response to be greater than 0.1 for the serotypes unique to V114.

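### Does the 87.7% power for participants aged 65 and over need restating because it is conditional on overall success and leaves out H3?

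*Combined protocol and SAP*

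**What the plan says.** Section 10.7.1.1 adds H1, H2 and H3 in participants aged 65 and over at the request of the Japanese regulator, and fixes how they are judged: "Comparisons for these objectives will use the same criteria used to assess the primary endpoints as detailed in Section 9.6.1 and Section 9.6.2". Section 10.7.1.2 refers back to 9.4, 9.6.1 and 9.6.2 for endpoints and methods.

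Section 10.7.1.3 requires at least 800 of the 1200 participants to be 65 or older. It gives power of 87.7% for noninferiority on the 13 shared serotypes and "superiority for the 2 unique serotypes based on OPA GMTs", and attaches the condition "conditional on the total planned sample size being able to meet the primary immunogenicity objectives described in Section 3". It puts the one-sided alpha at 2.5%.

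For the full population, 9.1 states: "The overall power for all the primary hypotheses is >90% at an overall 1-sided 2.5% alpha-level". Section 9.9.1 adds "Sample size is also driven by country-specific requirements (see Appendix 10.7 for details"). It describes the assumed H3 differences only as those "observed in V114-006 for the V114 unique serotypes, which are >0.1". Section 9.8 says "All hypotheses will be tested individually for each serotype at a 1-sided 0.025 alpha-level" and does not mention the ≥65 set.

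**The concern.** Three things look wrong together.

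- **Different events.** The overall figure is unconditional and covers H1 to H3. The ≥65 figure is conditional and covers H1 and H2. A reader who follows 9.9.1 to the appendix could take 87.7% as the chance of meeting the Japan objectives, a 12.3% risk of missing them. On the stated figures, the risk of missing either the overall objectives or the ≥65 GMT hypotheses could be as high as 21.1%, before ≥65 H3 is counted.
- **No testing order.** The power sentence hints that the ≥65 set comes after overall success, but no testing rule says so. If one shared serotype failed overall and the ≥65 set passed, the standing of the ≥65 result could be disputed after unblinding.
- **No H3 power.** H3 must also be met at ≥65, with about two thirds of the sample, and the only input given is that the differences exceed 0.1, which is the margin itself.

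At stake is whether the ≥65 quota is adequately justified. Type I error within the set is not in question: every comparison must pass at one-sided 0.025.

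**Working it through.** **Inputs.** From 9.9.1: 90% evaluability (540 per arm), shared-serotype GMT ratios from 0.78 to 1.86, unique-serotype ratios above 6.0, log-titer SDs from 1.33 to 2.25, and margins 0.50, 2.0 and 0.1. From 10.7.1.3: at least 800 aged ≥65, so 400 × 0.90 = 360 evaluable per arm at the minimum, and the 87.7%.

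**1. What the stated figures guarantee.** P(overall met and ≥65 GMT met) = 0.877 × overall power: 78.9% at 90%, 83.3% at 95%, 86.8% at 99%. The documents say above 90%, so 78.9% is a floor.

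**2. Reproducing 87.7%.** Per-serotype ratios and SDs are not given, so exact reproduction is impossible. Assume k equal, independent limiting shared serotypes at ratio 0.78 and a common effect across ages. Then δ = ln(0.78/0.50) = 0.4447, SE = SD × √(2/n), and power per serotype = Φ(δ/SE − 1.96). The ≥65 and overall statistics have correlation √(360/540) = 0.816. The SD is solved so that the conditional power is 0.877.

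For k = 1 the SD is 2.01. Overall: SE 0.1226, Φ(3.63 − 1.96) = 95.2%. At ≥65: SE 0.1501, Φ(2.96 − 1.96) = 84.2%. Both: 83.5%, and 83.5/95.2 = 87.7%.

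| k | SD | Overall GMT | ≥65 GMT, stand-alone | Both |
|---|---|---|---|---|
| 1 | 2.01 | 95.2% | 84.2% | 83.5% |
| 3 | 1.65 | 98.0% | 86.3% | 86.0% |
| 13 | 1.40 | 99.3% | 87.2% | 87.1% |

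Each SD lies within the 9.9.1 range, so 87.7% is credible. The k = 13 row is only an extreme, because 9.9.1 has the ratios running up to 1.86. Stand-alone GMT power is 0.5 to 3.5 points below 87.7%, and joint power 0.6 to 4.2 points below.

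**3. What the missing order is worth.** It matters only when the ≥65 set passes and the full population fails. With H3 certain, that probability is stand-alone minus both: 0.7, 0.3 and 0.1 points. If H3 is weak enough to pull overall power down to 90%, all three ≥65 hypotheses pass with 69.7%, 67.4% and 66.6% stand-alone against 68.5%, 66.3% and 65.4% in sequence, a gap of 1.1 to 1.2 points.

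**4. Is H3 likely to be that weak?** The 65% to 70% range needs overall H3 power of 90.6% to 94.5%, and hence 76.3% to 82.8% at ≥65. Assume log-normal fold rises, a GMT ratio of exactly 6 (a shift of ln 6 = 1.79 on the log scale), a comparator mean log fold rise from −0.5 to 1.5, and the unpooled normal approximation at 360 per arm. With SD 2.25 at both visits, fold-rise SD = 2.25 × √(2(1 − ρ)), where ρ is the Day 1 to Day 30 correlation.

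| Fold-rise SD | ρ | Difference in proportions | ≥65 H3 power, per serotype |
|---|---|---|---|
| 2.25 | 0.50 | 0.28 to 0.31 | at least 99.9% |
| 2.5 | 0.38 | 0.26 to 0.28 | at least 99.6% |
| 3.18 | 0 | 0.21 to 0.22 | 88% to 92% |

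In the last row, two independent serotypes pass together with 0.88² to 0.92², about 78% to 84%, close to the weak range. That corner needs zero correlation between visits, the largest SD at both, the smallest ratio allowed and both unique serotypes there at once.

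**The case for a change.** The best argument for a change is that H3 is a required ≥65 hypothesis with no stated power, and that 9.9.1 presents the appendix as part of the sample-size justification. The documents alone cannot exclude weak H3 power: the extreme corner in step 4 comes close to it, and non-normal titers could move the figures either way. Settling the order of testing after unblinding would also look post hoc, while a sentence now costs almost nothing.

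What stands is that the appendix is thin. It has no unconditional or joint power, no H3 proportions and no explicit order. What does not stand is that a reader is misled or a result put at risk. The qualifiers sit in the same sentence as the 87.7%. The natural reading of 10.7.1.1 is that these are additional objectives for one regulator, judged at the primary criteria, and the same analyses are run and reported whichever order is assumed. Joint error control over both populations is claimed nowhere, so inflation across the two sets is not a defect.

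Raising the ≥65 quota to 900 would add some power, but it would reduce the room for ages 50 to 64 from 1200 − 800 = 400 to 1200 − 900 = 300. That is a recruitment trade-off, and 800 is already a minimum.

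**Conclusion.** No change follows. The observations about the text are right: 87.7% is conditional, covers GMTs only, and is the sole ≥65 power figure. But it is labelled as such, it is consistent with the inputs in 9.9.1, and the 2.5% alpha statement holds for the set. Read without its condition, it overstates ≥65 GMT power by 0.5 to 3.5 points in models that reproduce it. The 78.9% is a lower limit, not an expected value. The unstated order is worth at most about 1.2 points. H3 power at ≥65 is probably high given a GMT ratio above 6, though the documents do not show it.

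These sizes assume 360 evaluable per arm, a common GMT ratio across ages, equal independent limiting serotypes and, for H3, log-normal fold rises. Followed as written, the plan gives the same ≥65 estimates, intervals and pass or fail results as it would with the extra detail. This is a gap that analysts can fill sensibly; a sponsor wishing to be fuller could state the order and the H3 inputs when the text is next revised.
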